7.3. Secondary Clinical Endpoints

All secondary endpoint analyses will use the ITT sample, unless otherwise specified, and will be assessed during the post-transplant follow-up period, which will be a minimum of 12 months.

7.3.1. Post-transplant Clinical Endpoints

Variable: Secondary incidence endpoints including:

- Chronic allograft dysfunction, defined as indicated for the primary endpoint
- Listing for re-transplant, defined as indicated for the primary endpoint
- Death, defined as indicated for the primary endpoint
- Primary Graft Dysfunction (PGD), defined at 0, 24, 48, and 72 hours post-transplant per Section 7.5.4 of the protocol
- Grade A Acute Rejection, reported locally as defined in Section 7.5.1 of the protocol

- Antibody Mediated Rejection of Grade II or III, reported locally as defined in Section 7.5.2 of the protocol
 - Additionally, if the data allow, AMR will be evaluated according to the 2016 ISHLT consensus guidelines published in the Journal of Heart and Lung Transplantation.

Analysis: For each of the above incidence endpoints, the proportion of subjects with events will be reported by treatment group with a corresponding 90% confidence interval, and for PGD and the rejection endpoints the treatment groups will be compared using a Chi-square or Fisher's Exact test. The incidence of grade 2 or higher PGD will be summarized overall and at each of the 4 time points separately. Additionally, for acute rejection and antibody mediated rejection, number of events per person time (e.g., year) will be estimated.

An example of SAS code to be used:

```
Proc freq;  
  tables treatment_group * endpoint / chisq measures cl alpha=0.1;  
run;
```

Variable: Incidence of meeting the tacrolimus variability threshold

Analysis: Among subjects who have at least 3 outpatient tacrolimus trough levels collected that are at least 3 months (i.e., greater than or equal to 3 months) post-transplant, an estimate of the standard deviation of tacrolimus levels will be produced for each subject. This estimate will be a rolling estimate (continually re-assessed) and may use up to 1 year worth of trough levels at any given time. The proportion of subjects with an estimated standard deviation at any time of 2.0 ng/mL or greater will be reported with a corresponding 90% confidence interval.

Variable: Incidence of completion of the Tacrolimus Variability Intervention (TVI)

Analysis: Among subjects who qualified for and agreed to participate in the TVI, the proportion of subjects who complete the intervention will be reported with a corresponding 90% confidence interval.

Variable: Magnitude of change in standard deviation of tacrolimus levels following intervention

Analysis: Among subjects who qualified for and agreed to participate in the TVI, the change in standard deviation of tacrolimus levels following the TVI will be examined. More specifically, a paired t-test will be carried out using the pre-intervention and post-intervention estimates of the standard deviation. An estimate of the mean difference between pre- and post-intervention standard deviation with a corresponding 90% confidence interval and p-value will be produced.

The value used for pre-intervention may be the same estimated standard deviation which qualified the subject for the TVI; however, if additional tacrolimus levels are recorded for a subject prior to their re-affirmation of consent for TVI participation, all outpatient tacrolimus levels in the year prior to commencement of the TVI will be used for estimating the pre-intervention standard deviation.

Likewise, the standard deviation value used for post-intervention will be estimated using all outpatient tacrolimus levels collected in the 180 days following completion of the TVI.

All estimates of the standard deviation pre- or post-intervention will adhere to the same conditions described earlier, which mandate at least 3 outpatient tacrolimus levels collected at least 3 months post-transplant.

Additionally, the change in standard deviation will be analyzed using the same paired t-test approach for pre-intervention vs. 180 days post-enrollment into the TVI, providing an assessment of change during the intervention.

Furthermore, attempts will be made to identify a set of “control” subjects for descriptive comparisons to subjects who enrolled and completed the TVI. These “control” subjects will at a minimum consist of subjects who qualified for but did not enroll in the TVI, and may be supplemented with subjects whose standard deviation exceeded 2.0 ng/mL but were not flagged due to enrollment in the TVI having been terminated. No formal statistical comparison of these two sets of subjects is planned.

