3.1. Description of Study Design

This is a phase 2, prospective, multi-center, double-blind, randomized, placebo-controlled clinical trial in which 50 primary pediatric lung transplant recipients will be randomized (1:1) to receive either induction therapy with anti-CD20 mAb (375 mg/m²) IV or placebo (IV day 0 and day 12 post-transplant) plus standard of care immunosuppression (thymoglobulin induction, tacrolimus or equivalent, MMF or equivalent, and steroids). The study will randomize 50 primary pediatric lung transplant recipients from seven participating centers. Subjects will be screened, consented, and enrolled while on the UNOS waitlist. When the recipient has received the transplant and is deemed hemodynamically stable, randomization will occur.

[figure not shown]

Figure 9: Study Design

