8.3. Randomization

Eligibility for randomization will be confirmed. Hematology (CBC with differential and platelet count) and serum chemistries will be obtained within 2 weeks of randomization.

Randomization will occur within 12 hours after returning to the ICU following transplant.

Randomization will only occur if there are still spaces available at the time of transplantation. If the targeted accrual has been reached at the time of transplantation the participant will be excluded from further procedures and randomization.

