12.8.2 DSMB Review

12.8.2.1 Planned DSMB Reviews

The Data and Safety Monitoring Board (DSMB) shall review safety data at least yearly during planned DSMB Data Review Meetings. Data for the planned safety reviews will include, at a minimum, a listing of all reported AEs and SAEs.

The DSMB will be informed of an Expedited Safety Report in a timely manner.

12.8.2.2 *Ad hoc* DSMB Reviews

In addition to the pre-scheduled data reviews and planned safety monitoring, the DSMB may be called upon for *ad hoc* reviews. The DSMB will review any event that potentially impacts safety at the request of the study principal investigator or DAIT/NIAID. In addition, satisfaction of any of the following **stopping rules** in study subjects at any time of follow-up in the treatment arms will trigger an *ad hoc* DSMB Safety Review:

- Any occurrence of confirmed PML.
- Incidence of death of 30% or more subjects.
- Incidence of at least mild acute rejection of 35% or more.
- Incidence of humoral rejection of 25% or more.
- Incidence of primary graft dysfunction of 50% or more.
- Incidence of PTLD of 5% or more.
- Incidence of infections of any type requiring hospitalization of 40% or more.

The thresholds for stopping rules involving subject-level incidence rates have been formulated based on an analysis of adverse events in the CTOTC-03 (NCT00891865) observational study of subjects who are similar to those in the control arm of this study. They will be evaluated routinely by the SACCC with the occurrence of any of the triggering events throughout follow-up of subjects within either randomized treatment arm. They will be implemented by comparing the exact lower 95% confidence limit on the currently observed subject-level incidence rate to the threshold rate described for that event in the stopping rule. If the lower confidence limit is greater than the threshold, the stopping rule will be considered to have been met and the Medical Monitor, DSMB and study PI will be notified.

Following are tables illustrating, for each stopping rule, the minimum numbers of subjects with the respective event that would meet the stopping rule for selected numbers of subjects within either randomized treatment arm:

Table 15: Minimum Numbers of Subjects with the Event in Either Randomized Treatment Arm that meet the Stopping Rule for Death with a Threshold of Concern of 30%

Number of Subjects with Event	Number of Randomized Subjects	Cumulative Incidence Rate	Lower 95% Confidence Limit

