13.4.4 Analyses of Secondary Endpoints and Safety Outcomes

All secondary endpoint analyses will use the ITT sample and will be assessed during the post-transplant follow-up period, which will be a minimum of 12 months.

Separately for each of the secondary incidence endpoints, we will compare the rituximab and control groups on the proportion of patients in each group with at least one episode of the endpoint by estimating the relative risk of the endpoint with its two-sided 90% confidence interval. The absolute risk difference with 90% confidence interval will also be estimated. These methods assume no, or very low rates of, death and re-transplant in the study period. However, if meaningful numbers of subjects have these outcomes, the risk ratio for each incidence endpoint can be estimated through a Cox proportional hazards model with the incidence endpoint as the outcome and right-censoring at death, re-transplant, or other loss to follow-up, following the modeling process described above for the primary endpoint.

Among subjects who are identified as qualifying for and agreeing to participate in the TVI, we will compare the rituximab and control groups on change in standard deviation of tacrolimus levels following the TVI (described in sections 5.3.3 and 8.4) using an analysis of covariance (ANCOVA) model, in which the standard deviation of tacrolimus levels following intervention is the outcome, and study group and pre-intervention standard deviation of tacrolimus levels are the predictors. The group effect with its 90% confidence interval will be estimated.

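### The SAP's overall PGD incidence counts a 0-hour grade that is effectively pre-treatment, and the PGD stopping rule names neither a grade nor a time

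*SAP*

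**What the plan says.** SAP 7.3.1 lists PGD as a secondary incidence endpoint, "defined at 0, 24, 48, and 72 hours post-transplant per Section 7.5.4 of the protocol". It adds: "The incidence of grade 2 or higher PGD will be summarized overall and at each of the 4 time points separately". For PGD and the rejection endpoints, "the treatment groups will be compared using a Chi-square or" Fisher's exact test; the sentence names no time point or measure. Protocol 13.4.4 compares the arms "on the proportion of patients in each group with at least one episode of the endpoint"; the planned estimate there is a risk ratio with a 90% interval.

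On sequence, Protocol 3.1 says: "When the recipient has received the transplant and is deemed hemodynamically stable, randomization will occur". Protocol 8.3 adds: "Randomization will occur within 12 hours after returning to the ICU following transplant". SAP 6.2 sets the same 12-hour limit for the first infusion. Protocol 7.5.4 refers to four time points without giving the hours, sets no sampling window, and takes the worst P/F ratio when several blood gases exist.

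The stopping rule in Protocol 12.8.2.2, also in both synopses, reads "Incidence of primary graft dysfunction of 50% or more". It gives no grade and no time, although PGD is graded 0 to 3 and the acute rejection rule in the same list does name a minimum severity. The thresholds are said to come from adverse events in the CTOTC-03 observational study.

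**The concern.** An outcome that compares arms should be able to respond to treatment. A grade taken at 0 hours post-transplant comes before randomisation and infusion on the stated sequence, so rituximab cannot change it. Once a child is positive at 0 hours, the overall measure is fixed at yes in either arm. It then cannot register later benefit or harm in that child. The overall contrast shrinks toward no difference in both directions, in a trial with about 25 children per arm.

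The stopping rule has a related gap. Without a grade or time, grade 1 PGD, or PGD seen only at 0 hours, could count toward a trigger. A trigger brings an ad hoc DSMB review and a temporary halt in enrolment, randomisation and dosing.

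**Working it through.** **Plan's own figure (Table 18).** The printed limits are one-sided 95% exact limits, the 0.05 quantile of Beta(x, n - x + 1). All ten reproduce to two decimals: 7 of 8 gives 52.93, and 13 of 18 gives 50.22. A two-sided 95% limit would not match (7 of 8 gives 47.35). The first row shows 5 events in 4 subjects, which is impossible. Its limit of 54.93 belongs to 5 of 5; 4 of 4 gives 47.29 and does not cross 50%.

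**Dilution.** Let p0 be the share with grade 2 or higher at 0 hours, and q the rate of new grade 2 or higher PGD by 72 hours in children free of it at 0 hours. Then

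overall incidence = p0 + (1 - p0) × q,

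and the risk difference is (1 - p0) times the difference in q. The documents give neither p0 nor q, so the values below are assumptions. The risk ratio (RR) for new PGD is 0.50 throughout.

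| p0 | q 20% v 10%: overall | RR | q 30% v 15%: overall | RR |
|---|---|---|---|---|
| 10% | 28.0% v 19.0% | 0.68 | 37.0% v 23.5% | 0.64 |
| 20% | 36.0% v 28.0% | 0.78 | 44.0% v 32.0% | 0.73 |
| 30% | 44.0% v 37.0% | 0.84 | 51.0% v 40.5% | 0.79 |
| 40% | 52.0% v 46.0% | 0.88 | 58.0% v 49.0% | 0.84 |

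**What dropping 0 hours recovers.** PGD present at 0 hours may still be present at 24 hours or later. Let s be the share that persists, assumed equal in the two arms. Then

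incidence at 24-72 hours = p0 × s + (1 - p0) × q.

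- p0 = 40%, q 20% v 10%, s = 50%: 0.20 + 0.12 = 0.32 v 0.20 + 0.06 = 0.26, RR 0.81. With s = 80%: 0.44 v 0.38, RR 0.86. With 0 hours counted, RR 0.88.
- p0 = 10%, q 30% v 15%, s = 50%: 0.05 + 0.27 = 0.32 v 0.05 + 0.135 = 0.185, RR 0.58. With s = 80%: 0.35 v 0.215, RR 0.61. With 0 hours counted, RR 0.64.

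The 0.50 is seen only in children free of PGD at 0 hours, which is why results by 0-hour grade are also needed. At p0 = 40% that stratum has about 25 × 0.6 = 15 children per arm.

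**Power.** The case most favourable to dropping 0 hours is a 24-72 hour grade independent of the 0-hour grade. Chi-square test, 25 per arm, two-sided 0.10:

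| 24-72 h rates | 0 h left out | 0 h counted, p0 = 20% | p0 = 40% |
|---|---|---|---|
| 30% v 15% | 35% | 22% | 16% |
| 40% v 20% | 46% | 30% | 21% |
| 50% v 25% | 57% | 41% | 29% |

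Persistence would narrow these gaps.

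**Stopping rule.** At n = 25 the rule needs 18 events (lower limit 53.8%). If the rule is checked after each subject up to 25, the chance that one arm crosses at some point depends on the true rate of whatever is counted as PGD:

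| Counted rate | 30% | 40% | 50% | 60% | 70% | 80% |
|---|---|---|---|---|---|---|
| Chance of crossing | 0.4% | 2.5% | 11% | 35% | 71% | 95% |

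A broad definition and a narrow one could therefore behave very differently.

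**The case against.** Four points on the other side have force.

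- A reader might infer that early benefit or harm is hidden. It is not: the same SAP section reports 24, 48 and 72 hours separately. Only the overall figure, and any test run on it, is affected.
- A reader might infer that the SAP tests the overall figure. It does not say so; the test is tied to no measure. Protocol 13.4.4 does plan a risk ratio on an any-episode basis, and counting 0 hours in it is the natural reading, but that is still a reading.
- That 0 hours precedes treatment follows from the sequence of events but is not stated. No clock or window is given, and with the worst P/F ratio used, a wide window could overlap an early infusion.
- Randomisation balances 0-hour events in expectation, so the comparison is not biased. PGD is one of several secondary endpoints, the protocol puts estimates and 90% intervals first, and power is low (35-57% above) even without dilution.

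On the stopping rule, a reader might infer that pre-drug PGD could end the study. A trigger leads to a review and a temporary halt, after which the DSMB makes a recommendation. Nor do the documents support simply matching the rule to a redefined endpoint. The 50% threshold rests on CTOTC-03, whose PGD grade and timing are not stated, and a changed definition could break that link.

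These points limit the concern but do not remove it. Nothing in either document excludes 0 hours from the overall measure or treats it as baseline, and the stopping rule's definition is missing.

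**Conclusion.** The point holds in a limited form. The overall PGD incidence includes an effectively pre-treatment grade, which dilutes the contrast without biasing it and leaves it unable to show any effect in children already positive at 0 hours. The measure used for the test is unspecified.

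The size cannot be taken from the documents. With 0-hour rates of 10-40% and new PGD halved from 20% or 30%, an RR of 0.50 in children free of PGD at 0 hours appears as 0.64-0.88. At 50-80% persistence, dropping 0 hours alone moves the two extreme scenarios only from 0.88 to 0.81-0.86 and from 0.64 to 0.58-0.61. The timing rests on the stated order of events, with no defined window for 0 hours.

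The stopping rule does lack a grade and a time, and it differs from the SAP endpoint, which uses grade 2 or higher. The passages must be reconciled.

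**What to change.** In SAP 7.3.1, before unblinding:

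- Make the compared PGD endpoint grade 2 or higher at any of 24, 48 or 72 hours, and say that the chi-square or Fisher test and the 90% intervals refer to it.
- Report the 0-hour grade as a baseline characteristic. Adjust for it (grade 2 or higher v lower) or stratify by it, and show the results by 0-hour grade.
- Keep the 0-hour summary and the summary over all four times as descriptive.
- State the clock and sampling window for each time point.

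All four grades are already planned, so no new data are needed. The price is one more covariate, or sparse strata, at about 25 per arm.

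For the stopping rule, state in Protocol 12.8.2.2 and both synopses the PGD grade and time that underlie the CTOTC-03-based 50% threshold, and explain any difference from the SAP endpoint. This needs an IRB-approved protocol amendment as well as SAP wording. The impossible first row of Table 18 can be corrected at the same time.

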2.1. Background and Scientific Rationale

Outcomes after pediatric lung

Pediatric lung transplantation is an accepted treatment for end-stage lung disease. Despite advancements in recipient selection, surgical techniques, prophylaxis against infection and development of new immunosuppressive regimens, annual reports from the International Society for Heart and Lung Transplantation (ISHLT) indicate no statistical improvement in long term outcome or survival for pediatric lung transplant recipients¹. Further, data from the United Network for Organ Sharing (UNOS) supports that while survival has improved marginally, improvements in short-term survival account for this difference². In addition, outcomes in both pediatric and adult lung transplantation are significantly worse than outcomes following transplantation of other solid organs. Despite increasing use of T-cell depleting induction therapies, 5-year survival has not been significantly impacted¹. Five year survival has only increased incrementally from 51% to 53% in the most recent report.

Bronchiolitis obliterans syndrome and morbidity/mortality

BOS is the primary and most significant cause of long term morbidity and mortality after human lung transplantation (LTx) and reports from two large centers have shown the prevalence of BOS is 60% to 80% in 5 years post LTx in adults³⁻⁶. The most recent statistics show 14% of pediatric patients develop bronchiolitis obliterans syndrome (BOS) within the first year after transplantation, which is unchanged from 5 years ago^{1,7}. The incidence of BOS within 4 years of transplant ranges from 31% in infants < 1 year at transplant to 54% in children ≥ 12 at transplant and up to 80% between 5 and 10 years in adults^{1,7-9}. Between 25 and 40% of lung transplant recipients will die directly or indirectly from BOS^{1,3}. While retransplantation for late lung allograft failure is feasible, limited organ availability can preclude rapid retransplantation and, more importantly, the survival after a second pediatric lung transplant is significantly worse than the primary transplantation particularly if performed within one year of the primary transplant¹⁰⁻¹³.

Immunologic basis for bronchiolitis obliterans syndrome

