13.4 Analysis Plan

The overall focus of our statistical analysis of the clinical portion of the study will be on the estimation of hazard ratios (HR) and risk ratios (RR) and their two-sided 90% confidence intervals comparing the rituximab and placebo groups on each endpoint of the study. Focusing on estimates and confidence intervals will allow us to assess the range potential efficacies as best we can within the limitations imposed by studying such a rare pediatric population.

Further detail describing the analysis plan will be contained in a Statistical Analysis Plan (SAP) that will be maintained by the SACCC and updated as necessary.

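### SAP 7.3.1 compares acute rejection and AMR between arms only by a test on ever/never proportions; it omits the protocol's relative risk, risk difference and optional Cox model, and has no rule for death before rejection

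*SAP*

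**What the plan says.** Protocol 13.4 puts the focus of the clinical analysis on "estimation of hazard ratios (HR) and risk ratios (RR) and their two-sided 90% confidence intervals". For the secondary incidence endpoints, protocol 13.4.4 compares the arms on the proportion with at least one episode by "estimating the relative risk of the endpoint with its two-sided 90% confidence interval", and adds: "The absolute risk difference with 90% confidence interval will also be estimated". It then gives the condition: "These methods assume no, or very low rates of, death and re-transplant in the study period". If meaningful numbers have these outcomes, it says a Cox model, right-censored at death, re-transplant or other loss, can be used.

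SAP 7.3.1 covers chronic allograft dysfunction (CAD), listing for re-transplant, death, primary graft dysfunction (PGD), acute rejection and AMR of Grade II or III. For each, "the proportion of subjects with events will be reported by treatment group with a corresponding 90% confidence interval". It continues: "for PGD and the rejection endpoints the treatment groups will be compared using a Chi-square or" Fisher's exact test. It also says that "for acute rejection and antibody mediated rejection, number of events per person time (e.g., year) will be estimated". The example code asks for association measures with 90% limits, but the text does not say which measure, if any, will be reported. No relative risk, risk difference or Cox model is named for these endpoints, and there is no rule for death or re-transplant before a rejection episode.

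Follow-up runs from 12 to 54 months (protocol 11.1). On mortality, protocol 2.1 states: "Five year survival has only increased incrementally from 51% to 53% in the most recent report".

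**The concern.** There are two separate problems.

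The first is the missing effect estimate. The protocol says that a relative risk and a risk difference will be estimated. Under the SAP text, acute rejection and AMR get an interval for each arm and a p-value between arms. With about 25 children per arm, a p-value says little about how large an effect the data allow, and that is the question the protocol sets itself.

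The second is death before rejection. A child who dies rejection-free can no longer be diagnosed with rejection. In a simple proportion over all children, that child sits in the denominator as a non-event. Randomisation balances potential follow-up between arms but not time alive. If rituximab prolongs survival, treated children have longer to be diagnosed, and the crude comparison moves against the drug even when the underlying rejection rate is unchanged. The protocol foresaw this by attaching a condition and an alternative. The SAP keeps the proportions without either.

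**Working it through.** The documents give no expected rate, sample size or power for acute rejection or AMR, so the plan has no figure of its own to reproduce here.

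**1. Is death rare enough?** Five-year survival is 53% (protocol 2.1). With a constant hazard, μ = −ln(0.53)/5 = 0.127 per year. Follow-up is taken as uniform on 1 to 4.5 years, from 3.5 years of accrual plus a minimum of 1 year. The expected share of controls who die is

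1 − (e^(−μ) − e^(−4.5μ))/(3.5μ) = 1 − (0.8808 − 0.5647)/0.4444 = 0.289,

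or about 7 of 25. That is not a very low rate.

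**2. How far does the crude comparison move?** Assumptions, none of them given by the documents for this comparison:
- Rituximab has no effect on rejection.
- The hazard ratio on death is 0.45 or 0.40. These are protocol 13.6 planning values for the composite endpoint, applied here to death.
- The one-year rejection risk is about 10% (hazard 0.1 per year), 25% or 35%. The last two borrow the stopping thresholds for humoral and acute rejection as illustrative values only.
- The rejection hazard λ is either constant or falls to one-fifth after year 1.

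For a constant hazard, the probability of rejection before death by time u is λ/(λ+μ) × [1 − e^(−(λ+μ)u)], averaged over u. Example with 25% one-year risk, λ = −ln(0.75) = 0.288:
- Control: 0.694 × (1 − 0.349) = 0.452.
- Rituximab, hazard ratio 0.45, so μ = 0.057: 0.834 × (1 − 0.411) = 0.491.
- Crude relative risk: 0.491/0.452 = 1.09.

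| Rejection hazard | One-year risk | Control | Rituximab (HR on death 0.45 / 0.40) | Crude RR |
|---|---|---|---|---|
| Constant | 10% | 19.8% | 21.8% / 22.0% | 1.10 / 1.11 |
| Constant | 25% | 45.2% | 49.1% / 49.5% | 1.09 / 1.10 |
| Constant | 35% | 57.8% | 62.3% / 62.7% | 1.08 / 1.09 |
| Mostly year 1 | 25% | 29.0% | 30.6% / 30.8% | 1.06 / 1.06 |
| Mostly year 1 | 35% | 39.9% | 42.0% / 42.2% | 1.05 / 1.06 |

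The relative risk is 1.05 to 1.11 where the rejection hazards are equal, a shift of about 2 to 5 percentage points. Mean time alive is 2.28 years in controls against 2.52 years with hazard ratio 0.45. If rituximab worsened survival (hazard ratio 1.5 on death), the crude relative risk for 25% and 35% one-year risk would be 0.93 to 0.96.

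**3. What does this do to the test?** The SAP states no test level, so two-sided 0.10 was assumed to match the 90% intervals. In 4,000 simulated trials per scenario (25 + 25, hazard ratio 0.45 on death, 25% or 35% one-year risk), Chi-square rejected in 10 to 14% and Cox censored at death in 8 to 10%, with median hazard ratio 1.00 to 1.02. Most of the Chi-square excess is small-sample behaviour. The exact binomial rejection rate with equal proportions is already 9.9 to 11.7%, and the shift from death raises it by only 0.3 to 1.5 percentage points. With a true rejection hazard ratio of 0.6 and 35% one-year risk, power was 23 to 24% for Chi-square and 25 to 36% for Cox.

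**4. Does a 12-month horizon help?** Applying the step 2 formula at u = 1, with 25% or 35% one-year risk, the relative risk under no effect on rejection is 1.03 to 1.04. The distortion shrinks because fewer children have died.

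**The case against.** **Crude proportions are also the protocol's default, and its Cox model is optional.** This stands. A reader might infer that the SAP removed a mandatory switch to Cox, but the protocol only says that Cox can be used. The relative risk and risk difference are different: the protocol commits to both.

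**The SAP is not silent on effect size or exposure.** Partly right. It gives 90% intervals per arm and person-time rates for both rejection endpoints, and its code requests association measures. But the rates carry no ratio, interval or comparison, and example code is not a prespecified estimate. For infections, SAP 7.3.2 does specify a rate ratio with a 90% interval and a follow-up offset.

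**This is a choice of estimand, not an error.** Largely fair. With balanced potential follow-up and no other loss, the crude proportion is a cumulative incidence with death as a competing event, averaged over follow-up. Cox censored at death targets a cause-specific hazard. Neither is wrong, but the SAP does not say which question it answers, and the averaging horizon depends on when each child was transplanted.

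**It does not reach all secondary incidences.** Correct. CAD, listing and death are not tested in SAP 7.3.1 and have time-to-event analyses in SAP 7.2.2 and 7.2.3. PGD is assessed within 72 hours, so later deaths hardly affect it; for PGD only the missing relative risk and risk difference matter.

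**Few events may occur.** Protocol 13.4.3 and SAP 7.2.3 expect little to no events for at least one primary component. They do not say that component is death, and the survival figure suggests otherwise.

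**Conclusion.** The point holds for acute rejection and AMR, and for PGD as far as the missing effect estimates go. The omission of the relative risk and risk difference is a plain departure from protocol 13.4.4 and needs no simulation to show. The handling of death is an unstated rule with a modest, conditional consequence: a crude relative risk of about 1.05 to 1.11 instead of 1.00. That range rests on a constant death hazard from 53% five-year survival, a hazard ratio of 0.40 to 0.45 on death, and assumed rejection rates. Its sign depends on whether rituximab lengthens or shortens survival.

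Three stronger readings are tempting and not supported:
- The 30% death figure in protocol 12.8.2.2 is a threshold for safety review, compared with a lower confidence limit. It is not an expected mortality.
- Relative risks near 1.2 appear only if most or all of the composite hazard is treated as death. With 53% event-free at two years and a constant hazard, that would mean five-year survival of 0.53^2.5 = 20%, against the 53% stated.
- A crude relative risk nearer 1 than the hazard ratio is not by itself a sign of bias from death. Hazards of 0.2 and 0.1 per year, a hazard ratio of 0.50, give a relative risk of 0.58 over this follow-up with no deaths at all.

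These are secondary endpoints in a 50-patient phase 2 trial. The change is worth making before unblinding; it does not threaten the primary analysis.

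**What to change.** In SAP 7.3.1:
1. For PGD, acute rejection and AMR, report the relative risk and the risk difference with 90% confidence intervals, as protocol 13.4.4 states.
2. For acute rejection and AMR, state how death and re-transplant before a first episode are handled in the proportions and in the person-time.
3. For the same two endpoints, add the protocol's Cox model, censored at death, re-transplant or loss, and label its result a cause-specific hazard ratio with 90% interval.
4. Beside it, give 12-month cumulative incidence by arm with death as a competing event. Every child is due at least 12 months of follow-up, so this puts the risk on a fixed horizon.
5. Keep the Chi-square or Fisher p-values as supportive.

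No change is needed here to the time-to-event analyses of CAD, listing and death. The cost is SAP wording and minor programming, with no new data collection.
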